Despite ample research documenting the safety and efficacy of perioperative TXA in patients undergoing arthroplasty, there is no known clinical trial focusing on TXA's use in musculoskeletal oncology patients undergoing endoprosthesis reconstruction. Nonetheless, TXA is used within the musculoskeletal oncology community, with its use varying from surgeon to surgeon. Surgeons who use TXA do so with the intent of limiting perioperative blood loss and transfusion rates in these high blood-loss procedures. However, without clinical trial to support its use in this cohort, these patients, who tend to have an increased number of comorbidities, could be inheriting an increased risk of perioperative complication without the benefits documented. Conversely, patients within this cohort that do not receive TXA could be missing out on the clinical benefits of TXA seen in patients undergoing arthroplasty. This randomized clinical trial will determine the efficacy of tranexamic acid in musculoskeletal oncology population who underwent wide local excision and reconstruction with endoprosthesis and will result in the formation of a guideline about its efficacy in reducing blood loss and adverse events that can be resulted by the use of tranexamic acid in the musculoskeletal oncology population.

Objectives:

To determine the efficacy of tranexamic acid in musculoskeletal tumor who underwent wide local excision and reconstruction with endoprosthesis and determine adverse events that can be resulted by the use of tranexamic acid.

Primary outcome measures:

Blood loss in a surgical patient can be monitored by:

- Drop-in hemoglobin in 72 hours
- The number of transfused PRBC unit
- 72-hour total blood loss as calculated by hemoglobin balance method

Hemoglobin balance method:

The Hemoglobin - balance method is based on the balance of Hemoglobin during the perioperative period of surgery. It is regarded as an important method with intuitive expressiveness and high accuracy and often addresses contemporary clinical issues [14]

$Hb_{\text{loss total}} = BV \times (Hb_i - Hb_e) \times 0.001 + Hb_t$	$Hb_{\text{loss total}}$ (g): The loss volume of Hb
$V_{\text{loss total}} = 1000 \times Hb_{\text{loss total}} / Hb_i$	Hb_i (g/L): The Hb value before surgery
Generally, 1 U banked blood is considered to contain 52 ± 5.4 g Hb[5]	Hb_e (g/L): The Hb value after surgery;
	Hb_t (g): The total volume of blood transfusion

Secondary outcome measures:

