- Thromboembolic events: to be observed over six weeks from the date of surgery
- Hospital stay
- drain output till 72 hours

Methodology

Study Design: A Randomized control trial (RCT)

Setting: Department of surgical oncology, Shaukat Khanum Memorial Cancer Hospital and Research Center, Lahore.

Sample size:

Sample size was calculated on the basis of previous study published by Haase, Douglas R. in 2020. Mean post-operative blood loss in TXA group and non TXA were 981 ± 290 mL and 1542 ± 394 mL, respectively. [02] At 80% power, 95% confidence interval, assuming 10% drop out rate, a total of 36 patients included in this study divided into two groups (18 in each group, TXA versus non TXA) would be required in this study.

Sample selection:**Inclusion criteria:**

Patients with primary or metastatic bone tumors who underwent a resection and an endo-prosthetic reconstruction of the proximal femur, distal femur, proximal tibia and proximal humerus. All patients will be tested for liver function using PT (INR), renal function by serum creatinine and Marrow function by CBC

Exclusion Criteria:

- Patient with a congenital or acquired coagulopathy
- Severe renal or liver insufficiency
- Previous thromboembolic condition
- A patient who received perioperative plasma product
- Pelvic tumor
- Patient who is taking anti-coagulant before surgery
- Patient allergic to tranexamic acid

Enrollment duration: Being a dedicated cancer center, a large number (30-40 per year) of Limb salvage surgeries are performed at Shaukat Khanum Memorial Cancer Hospital. The above-given sample size can therefore be achieved in 10 months.

Dose of tranexamic Acid: A single dose of tranexamic acid will be given intravenously at time of induction according to body weight i.e., 15 mg/kg

Anti-coagulation Protocol: All limb salvage patients started on anticoagulant Injection Enoxaprin subcutaneously after 24 hours of surgery according to body weight i.e. 1.5 mg/kg. Enoxaprin converted to oral tablet Aspirin 75 mg on discharge for 4 weeks.

Study Duration: 12 months after the start of enrollment.

In house admission: Limb salvage surgery patients remain admitted on the floor for an average of 5 days

Follow up Schedule: Physical follow up in clinic 2 weeks after surgery (as per institutional guidelines) and a second follow up at 4 weeks after surgery

Randomization: Intraoperative randomization, patients would be allocated to either of the groups by selecting names from sealed envelopes.

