Type of randomization: Computerized block randomization. This will ensure a similar number of patients in both groups. Patients will have their names written on an envelope with contents of the envelope indicating whether tranexamic acid should be given or not. Only one member of research team will be aware of the contents of the envelope, who will not be present in Operation Theater at the time of surgery and will not take part in data collection. Patient in control group will be given 10 cc of normal saline as as placebo.

Blinding: It will be a triple-blind trial since the patients will be unaware of the group to which they have been randomized. The statistician carrying out data analysis and examiners/interviewers carrying out clinical examinations/interviewing patients will also be unaware of the status of tranexamic acid.

Minimizing Bias: It is not possible to eliminate bias altogether. However, the performance bias of the operating surgeon will be limited by not revealing the contents of the sealed envelope. The interviewer's bias will be limited by ensuring that the interviewer is not aware of tranexamic acid status at the time of the interview and by ensuring a standardized interaction between the patient and interviewer.

Intervention: Surgeon who will carry out Limb salvage surgeries, will be a consultant with > 5-year experience in Limb salvage. A single standardized technique will be used in all of the patients.

There is a difference of opinion about the use of tranexamic acid in surgeons at SKMH and both surgical options are practiced. The trial will therefore pose no additional risks to the patients.

References

- Wei W, Wei B: Comparison of topical and intravenous tranexamic acid on blood loss and transfusion rates in total hip arthroplasty. J Arthroplasty 2014;29:2113-2116

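### The perioperative-plasma exclusion is not tied to allocation and no analysis population is defined, so a randomised, treated patient could be dropped for an event that may follow from bleeding

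*Combined protocol and SAP*

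**What the plan says.** The protocol's Exclusion Criteria contain seven items. One is "A patient who received perioperative plasma product", with no start, no end and no link to allocation. Another item in the same list does carry a time limit: "Patient who is taking anti-coagulant before surgery".

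The word perioperative is not defined. The section on the hemoglobin balance method, which yields one of the primary outcomes, describes that method as "based on the balance of Hemoglobin during the perioperative period of surgery" and compares hemoglobin before and after surgery. The Introduction also uses the word for the giving of TXA.

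On timing, the dose section says "A single dose of tranexamic acid will be given intravenously at time of induction", while the Randomization section says "Intraoperative randomization, patients would be allocated to either of the groups by selecting names from sealed envelopes".

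The Statistical Analysis Plan names software, effect measures, tests and a significance level. It defines no analysis population and has no rule for a patient who is found to meet an exclusion after randomisation. The Sample size section makes an allowance, "assuming 10% drop out rate", without saying what counts as a drop-out. The Proforma records red-cell units within 72 hours but has no field for plasma.

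**The concern.** An exclusion is harmless to the randomised comparison when it depends only on what is known before allocation. Plasma given before allocation is a legitimate baseline exclusion and is not disputed here. Plasma given afterwards is different. It may be a response to bleeding, and bleeding is what the trial measures and what TXA is meant to change. Removing patients for it selects on something close to the outcome, and the selection can fall unequally on the two arms even when everyone is blinded and one rule applies to all.

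Normally an analysis-set definition would block this by keeping every randomised patient in the allocated group. This plan has none, so nothing in it prevents the removal. With 18 patients per arm, two or three removals from one side can shift the estimated effect. The protocol expects the result to feed a guideline on efficacy, so the estimate matters as well as the p-value.

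**Working it through.** **1. What the wording allows.** Two readings are open.

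- *Baseline only.* The item stands in a list of selection criteria, and the other six can be settled before surgery. The protocol sometimes uses perioperative for the giving of a drug.
- *Through and after surgery.* This is the ordinary meaning of the word. The protocol uses it this way for the hemoglobin method, and the anticoagulant item shows that the list states a pre-surgery limit when one is meant.

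The text does not settle which is meant. Dosing at induction and randomisation during the operation do not agree with each other. Under either, plasma given later in surgery or on the ward comes after allocation.

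**2. Inputs.** From the Sample size section: TXA 981 (SD 290) mL, non-TXA 1542 (SD 394) mL, 18 per group. The difference is 1542 − 981 = 561 mL. These are figures for post-operative loss, used here as a stand-in for 72-hour total loss. The documents give no indication for plasma and no rate of use, so every exclusion rate below is an assumption.

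**3. The plan's own figure.** Pooled SD = √((290² + 394²)/2) = 345.9 mL. At two-sided 0.05 and 80% power, n = 2 × (1.96 + 0.84)² × 345.9² / 561² ≈ 6 per group, and 6/0.9 rounds up to 7, or 14 in total. The stated 36 is not reproduced. That is a separate matter, but it explains why power is so high: with 18 per group the t-test has 99.7% power at the planned effect.

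**4. Same rule in both arms, planned effect.** Assume normal losses, and let the probability of plasma, and so of exclusion, rise with loss x as 1/(1 + exp(−(x − c)/w)). Here w sets how closely plasma tracks loss (small w, closely), and c is solved to give the chosen overall exclusion rate. Arm means among those kept come from numerical integration.

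| Excluded overall | w (mL) | c (mL) | Excluded, TXA v control | Difference among those kept | Change from 561 mL |
|---|---|---|---|---|---|
| 2% (0.7 of 36) | 150 | 2383 | 0.06% v 3.9% | 533 mL | −5% |
| | 300 | 2754 | 0.4% v 3.6% | 545 mL | −3% |
| | 600 | 3763 | 1.1% v 2.9% | 555 mL | −1% |
| 5% (1.8 of 36) | 150 | 2158 | 0.2% v 9.8% | 501 mL | −11% |
| | 300 | 2432 | 1.2% v 8.8% | 525 mL | −6% |
| | 600 | 3181 | 2.8% v 7.2% | 547 mL | −3% |
| 10% (3.6 of 36) | 150 | 1955 | 0.8% v 19.2% | 455 mL | −19% |
| | 300 | 2158 | 2.9% v 17.1% | 498 mL | −11% |
| | 600 | 2711 | 5.8% v 14.2% | 534 mL | −5% |

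The 10% row equals the plan's drop-out allowance; it is not an estimate of plasma use. Simulated power (two-sided t-test at 0.05) is about 99% or more at 2% and 5% excluded, and between 97.5% and 99.2% at 10%.

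**5. Same rule, no TXA effect.** Both arms have the same distribution and lose the same fraction, so the expected difference stays at zero.

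**6. Different rule by arm, no TXA effect.** Set both arms to 1542 (SD 394) mL and lower c by 300 mL in the TXA arm only (an assumption). The apparent benefit is 2 to 18 mL at 2% excluded overall and 10 to 56 mL at 10%. If c is lowered in the control arm instead, the sign reverses.

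Hemoglobin drop and red-cell units, the other two primary measures, are not quantified.

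**The case against.** The strongest reply is that no sentence in the plan says a randomised patient is withdrawn, replaced or left out of the analysis because of plasma. The criterion sits under sample selection beside six baseline items and may simply be loosely worded. Its past tense proves little, since the SAP also uses the past tense for work not yet done. This stands as far as it goes. A reader might infer that the plan requires post-treatment exclusion, and the documents do not support that. They permit it and contain nothing to prevent it.

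A reader might also infer that the exclusion could manufacture a benefit for TXA. That needs plasma use to differ by arm for reasons other than bleeding, and the Blinding and randomisation text makes this unlikely. Only one team member knows the envelope contents, and that person is neither in theatre nor collecting data. Controls receive saline as placebo, and "the performance bias of the operating surgeon will be limited by not revealing the contents of the sealed envelope". The possibility is not fully closed. The statement "It will be a triple-blind trial since the patients will be unaware of the group to which they have been randomized" is extended to the statistician and the examiners or interviewers but does not name whoever orders plasma, and the plan does not say who prepares the study drug. Still, nothing in the documents points to an arm-specific threshold, so step 6 is a boundary case and not a forecast.

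Finally, under a common rule the bias is conservative or nil and power hardly moves. That is correct, and it limits the severity. It does not remove the case for a clarification that costs almost nothing.

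**Conclusion.** The concern holds as a defect of wording and of analysis-set definition. The plasma exclusion is not tied to allocation, and the SAP has no rule that would keep a randomised patient who receives plasma later. Confidence in that is high.

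The consequence is conditional. If plasma follows bleeding, one rule applies to both arms and TXA works, the effect on blood loss is understated, illustratively by 1% to 19% for 2% to 10% excluded. Confidence in that direction is moderate. Confidence in the size is low, because the rates, the logistic form and the normal distributions are all assumed. The figures do not support a claim that the trial would miss the planned effect, since power stays at about 97% or more.

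Severity is minor to should-fix. It rests mainly on the missing rule to analyse all randomised patients, which would matter for any post-randomisation loss and not only for plasma.

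**What to change.** - **Exclusion Criteria:** keep the perioperative scope but limit the item to plasma given before randomisation, and have the trial team set the start of the window. Without a start point, the item would also catch plasma given years earlier.
- **SAP:** state that every randomised patient is analysed in the allocated group, whatever plasma is given later.
- **Proforma and reporting:** add a plasma field (units and time) and report plasma use by arm. A participant-flow report could show exclusions by arm, but without this field plasma use would have to come from other records.
- **Timing:** reconcile the passages on intraoperative randomisation and study drug at induction, so that the phrase before randomisation has one meaning.

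The cost is a one-line protocol amendment, one SAP sentence and one Proforma field, plus the timing reconciliation. The downside is that a few patients whose bleeding was also modified by plasma stay in the analysis. If the criterion was always meant as a baseline one, the rewording changes nothing in practice.

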- Femur _____
- Tibia _____
- Other

Group:

- Tranexamic Acid Given
- Tranexamic Acid Not Given

Length of Bone Resected _____ **Cm**

Wound Healing: (Satisfactory / Unsatisfactory)

Preoperative Hemoglobin _____gms

Preoperative INR _____

Intraoperative Blood Loss: _____mls

Postoperative Hemoglobin after 24 Hours _____gms

Postoperative Hemoglobin after 72 Hours _____

Number of PRBC Transfused Within 72 Hours of Surgery _____

Blood Loss Calculated By Direct Hemoglobin Method _____

Drain Output in 72 Hours: _____mls

Any Thromboembolic Event: _____

Status of Ambulation:

STATISTICAL ANALYSIS PLAN:

Statistician independently pooled data from each case then conducted statistical analysis using SPSS Descriptive data are presented as mean \pm standard deviation (*SD*). Odds ratio (*OR*) with 95% confidence intervals (*CI*) or mean differences (*MD*) with 95% *CI* were calculated for dichotomous and continuous outcomes, respectively. Numerical and measured data were compared using a *t*-test and χ^2 -test, respectively. An appropriate power and sample size calculator was used to calculate statistical power. The following parameters were used in the calculations: α , probability of a type I error for a two-sided test; P_0 , probability of exposure in controls; N , number of patients; m : ratio of control to experimental subjects; and Ψ , odds ratio of exposure in experimental subjects relative to controls. $P < 0.05$ was considered significant.

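### The plasma exclusion has no pre-surgery limit and the SAP names no analysis population, so randomised, dosed patients could be removed for an event linked to bleeding

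*Combined protocol and SAP*

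**What the plan says.** - **Exclusion Criteria.** One of the seven items is "A patient who received perioperative plasma product". Its only timing word is the adjective. Another item in the same list does carry a limit: "Patient who is taking anti-coagulant before surgery".
- **Hemoglobin balance method.** The method is described as "based on the balance of Hemoglobin during the perioperative period of surgery", and its formula runs from the haemoglobin value before surgery to the value after it.
- **Dose of tranexamic Acid; Randomization.** "A single dose of tranexamic acid will be given intravenously at time of induction". Randomisation is described as intraoperative.
- **Outcomes.** All three primary measures concern blood loss: haemoglobin drop in 72 hours, red-cell units, and calculated 72-hour loss. Among the secondary outcomes is "Thromboembolic events: to be observed over six weeks from the date of surgery".
- **Statistical Analysis Plan.** On who is analysed, the only text is "Statistician independently pooled data from each case then conducted statistical analysis using SPSS". There is no intention-to-treat statement, no rule for exclusions after randomisation, and no rule for missing data.
- **Proforma.** It has a field for "Number of PRBC Transfused Within 72 Hours of Surgery" but none for plasma.

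**The concern.** An eligibility rule protects a randomised comparison only if it is settled before allocation and treatment. Plasma given in theatre or on the ward comes after the induction dose. The Introduction expects massive bleeding in these operations, so plasma may well be a response to it. If tranexamic acid reduces bleeding, fewer treated patients would need plasma, and removing recipients would take heavy bleeders mainly from the control arm. The arms left for analysis would no longer be the randomised arms. Blinding does not prevent this, because the removing event can itself depend on treatment.

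The blood-loss estimate is at stake, since the trial is meant to inform a guideline. The safety count is at stake too, since adverse events are a stated objective and there are only 36 patients.

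**Working it through.** **Step 1: timing, from the text.** The list limits anticoagulants to use before surgery and sets no such limit on plasma. The haemoglobin-balance section uses the same adjective for a span that ends after surgery. Drug or placebo goes in at induction, so allocation must be known by then, and plasma given for surgical bleeding comes later. No section keeps a recipient in the analysis, and the proforma would show neither that plasma was given nor when.

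**Step 2: what the plan's figures allow.** The documents give no plasma rate, trigger or threshold, so there is no plan figure for this point to reproduce. The nearest is the total of 36. From the stated means and SDs, the root-mean-square SD is √[(290² + 394²)/2] = 345.9 mL, and n per arm = 2 × (1.96 + 0.84)² × 345.9² / 561² = 5.96, so 6. Then 6/0.9 rounds up to 7, a total of 14 (18 with the exact t calculation). The stated 36 is not reproduced. That is a separate matter, but it explains why power has room to spare below.

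**Step 3: illustration under an assumed trigger.** Inputs from the Sample size section: control 1542 (SD 394) mL, TXA 981 (SD 290) mL, 18 per arm, difference 561 mL. Assumptions: these values, described there as post-operative loss, stand in for the primary outcome; losses are normal; everyone above a cut-off T receives plasma and is removed.

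- Standard error of the difference = √(394²/18 + 290²/18) = 115.3 mL.
- With a = (T − mean)/SD, the fraction removed is 1 − Φ(a), and the mean of those who remain is mean − SD × φ(a)/Φ(a).
- Example, T = 2,000 mL. Control: a = 458/394 = 1.162, removed 12.3%, remaining mean 1450.9. TXA: a = 1019/290 = 3.514, removed 0.02%, remaining mean 980.8. Difference 470.1 mL, a loss of 90.9 mL, which is 16.2% of 561 and 0.79 standard errors.

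| Assumed T (mL) | Controls removed, of 18 | TXA removed, of 18 | Difference left (mL) | Shrinkage |
|---|---|---|---|---|
| 2,500 | 0.14 | about 0 | 552.8 | 1.5% |
| 2,300 | 0.49 | about 0 | 535.6 | 4.5% |
| 2,250 | 0.65 | about 0 | 528.6 | 6% |
| 2,000 | 2.2 | 0.004 | 470.1 | 16% |
| 1,750 | 5.4 | 0.1 | 369.5 | 34% |
| 1,500 | 9.8 | 0.7 | 243.6 | 57% |

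**Step 4: inference.** Simulated trials with a pooled t-test at two-sided 5% gave coverage of the true 561 mL by the 95% interval of about 88% at T = 2,000, 94% at 2,300 and 95% at 2,500. Power was 98.6%, 99.6% and 99.7%, against 99.7% with no removal. This reassurance on power does not extend to the lowest cut-offs: at 1,500 mL only about 8 controls (18 − 9.8) would remain, with less than half the difference.

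**Step 5: is the sharp cut-off essential?** No. If the chance of plasma instead rises smoothly with loss (logistic, scale 200 mL), a midpoint of 2,250 mL leaves 512 mL and a midpoint of 2,000 mL leaves 469 mL. Removal is still far heavier among controls (9.1% against 0.5%, and 19.2% against 1.6%).

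**The case against.** **A screening rule was probably meant.** The item sits under Sample selection, the other six exclusions can all be known before surgery, and nothing orders the withdrawal of a randomised patient. The adjective is also used loosely elsewhere: the Introduction applies it to giving the drug, which in this trial is one dose at induction. The SAP's reference to each case could even be taken to mean that everyone is included. This stands in part. The wording permits the post-dose reading without compelling it, so a reader who infers that the plan requires dosed patients to be removed goes beyond the text. But the text does not confine the rule to screening either, and the SAP wording is too thin to act as a safeguard.

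**The size depends on the assumed cut-off.** This stands. Shrinkage runs from 1.5% to 57% across the cut-offs tried, and no document favours one of them. A reader might infer a demonstrated, material bias, or a false finding of benefit. The documents support neither: the effect may be negligible, and in this model it runs toward no effect.

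**Loss from the safety count is an inference.** This also stands. Nothing says that follow-up or event counting stops for an excluded patient. Equally, nothing says that it continues.

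**There may be a good reason to exclude plasma recipients.** The blood-loss formula has a transfusion term but nothing for plasma. If plasma dilutes the post-operative haemoglobin by δ, calculated loss rises by blood volume × δ / pre-operative haemoglobin, so dilution by 1% of the pre-operative value adds 1% of blood volume. That error has a direction and is not just noise. It calls for a sensitivity analysis, and it does not justify removing patients after treatment.

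**Conclusion.** The point holds as a gap that should be closed, with medium confidence. The exclusion has no pre-surgery limit, its ordinary meaning reaches events after randomisation and dosing, those events may follow from the primary outcome, and no analysis population is named to keep the affected patients in. Applied as worded, it could bias the blood-loss difference and could take patients out of the thromboembolic count.

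The size cannot be derived from the documents. Under the assumptions above it ranges from negligible (8 mL, 0.07 standard errors, at 2,500 mL) through material (91 mL, 0.79 standard errors, at 2,000 mL) to larger at lower cut-offs, toward no effect throughout. What does not depend on the exact cut-off is the asymmetry: with the planning means and SDs, removing heavy bleeders falls mostly on controls. For cut-offs of 2,000 mL or more, the risk is to the effect estimate and the safety count, and hardly to significance.

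**What to change.** 1. Reword the exclusion to: *plasma product received before randomisation and study-drug dosing at induction*. Naming both events matters, because the protocol calls randomisation intraoperative while the dose is given at induction, so randomisation alone is not a clear cut-off.
2. Add to the SAP: *Every randomised patient is analysed in the allocated group for blood loss and thromboembolic events, whatever plasma is given.* The proforma's Group item records drug given or not given, so allocation should come from the randomisation list.
3. Add plasma units and time of administration to the proforma.
4. Add a simple sensitivity analysis of blood loss with and without plasma recipients, keeping the all-randomised analysis as primary. The version without them carries the selection problem described here and should be read only as a check on dilution.

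The cost is one reworded criterion, two SAP sentences and one proforma entry. The sample size does not change. The downside is that recipients stay in the primary analysis, where dilution may inflate their calculated loss; item 4 shows how far that matters.

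### Allocation concealment is not assured: the mechanism is described in two ways, and the one person who knows the envelope contents is not kept out of recruitment or of matching names to envelopes

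*Combined protocol and SAP*

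**What the plan says.** All the relevant text is in the Methodology part of the protocol; the statistical analysis plan adds nothing on allocation.

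- **Randomization:** "Intraoperative randomization, patients would be allocated to either of the groups by selecting names from sealed envelopes".
- **Type of randomization, method:** "Type of randomization: Computerized block randomization. This will ensure a similar number of patients in both groups". No block size or stratification factor is given.
- **Type of randomization, envelopes:** "Patients will have their names written on an envelope with contents of the envelope indicating whether tranexamic acid should be given or not".
- **Type of randomization, who knows:** "Only one member of research team will be aware of the contents of the envelope", and this is a person "who will not be present in Operation Theater at the time of surgery and will not take part in data collection".
- **Minimizing Bias:** "the performance bias of the operating surgeon will be limited by not revealing the contents of the sealed envelope".
- **Dose of tranexamic Acid:** "A single dose of tranexamic acid will be given intravenously at time of induction according to body weight". This bears on when the envelope has to be opened.

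The text does not say:

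- whether envelopes are opaque or numbered, or whether they must be used in order;
- who generates the list;
- who writes the name on the envelope, and whether this comes before or after consent and confirmed eligibility;
- whether the person who knows the contents also screens or recruits;
- who opens the envelope.

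**The concern.** Two things need attention. First, picking names and following a block sequence are different operations. A block list fixes the order of assignments in advance, and it keeps its properties only if each new patient takes the next entry. Nothing in the text makes that link.

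Second, each assignment is tied to a named patient and is known to a team member before treatment. If that person can influence who is entered, when they are entered, or which envelope receives which name, patients can be steered to an arm.

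Steering of this kind is selection bias. It acts before treatment, so blinding of patients, examiners and statistician does not remove it, and neither does an unadjusted comparison of means. The conditions make it worth guarding against. There are 36 patients over four anatomical sites with no stratification stated. The closing paragraph of the Intervention entry records that surgeons at the centre disagree about using the drug. The Introduction says that the result is meant to lead to a guideline.

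**Working it through.** No figure in the plan depends on the allocation mechanism, so the check is a comparison of texts.

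**Step 1: do the two descriptions state one procedure?** The Randomization entry has names selected from sealed envelopes during the operation. The next entry has a computerised block list, with the assignment inside an envelope that bears the patient's name. They can be joined as a computer list delivered by envelope. The joining rule, that the next patient takes the next envelope, is missing, and the word for selecting points away from it. The wording is therefore inconsistent, but two different methods are not proven.

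**Step 2: what does each stated safeguard protect?**

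| Safeguard in the protocol | Bias it addresses | Does it bear on who gets which envelope? |
|---|---|---|
| Envelope is sealed | Foreknowledge by those without access to the contents | Yes, in part; opacity and numbering are not stated |
| Contents not revealed to the surgeon | Performance bias, by the protocol's own description | Only as regards the surgeon |
| Person who knows the contents is absent from theatre | Performance bias | No |
| The same person does not collect data | Detection bias | No |

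No row bars the person who knows the contents from recruitment, eligibility decisions or attaching names to envelopes.

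**Step 3: when are names attached?** The Enrollment duration entry plans 36 patients over 10 months, so 36 / 10 = 3.6 patients a month on average. Patients arrive one at a time, and names can be attached only as they become known. Whether an envelope is filled before or after it is named is not stated. If the next list entry always goes to the next eligible patient, nobody chooses. If the order is free, somebody can. The text allows both.

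**Step 4: why block size belongs in the fix.** No block size is given, so these figures rest on assumed sizes. Suppose the size is fixed and known, and past assignments are known. In a block of 2 the second assignment is certain, so 1/2 are fully predictable, and a best guess is right (0.5 + 1)/2 = 75% of the time. Enumerating all balanced blocks of 4 and 6 in the same way gives 33% and 25% fully predictable, with best guesses right 71% and 68% of the time. Blinding should keep past assignments from recruiters, so this is a reason to withhold the block size and not an estimate of bias.

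**Step 5: timing.** Randomisation is called intraoperative, while the dose is tied to induction. The two entries must be reconciled, because together they determine when the envelope has to be opened.

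**The case against.** The best defence is that this is an ordinary envelope scheme, loosely worded. The two entries stand next to each other, and the second describes the named envelopes directly under the computerised block heading. The envelopes are sealed. Someone has to hold the list in any such scheme, and here it is one person, kept away from surgery and data collection. All of that stands, and it rules out several stronger readings.

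- A reader might infer that allocation is not concealed. Sealed envelopes and a single list holder do not show that.
- A reader might infer that envelopes are filled before they are named, so that a person who knows the contents picks the match. The order of filling and naming is not stated.
- A reader might infer that the two entries would produce different allocations. They can be read as one scheme.
- A reader might try to size the bias. From the sample-size entry, the averaged SD is √((290² + 394²)/2) = 346 mL and the planning difference is 1542 − 981 = 561 mL. An assumed shift of 0.25 to 0.5 SD would be 86 to 173 mL, or 15% to 31% of 561 mL. The shift is chosen, not derived from anything in the documents, so these figures say nothing about this trial.

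What the defence does not answer is Step 2. The restrictions on the person who knows the contents protect the conduct of surgery and the collection of data, not entry into the trial.

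**Conclusion.** The point holds in this form: allocation concealment is not assured, and the mechanism is inconsistently described. It is more than an omitted detail, because the procedure as stated (names selected, envelopes bearing names, contents known to someone not barred from recruitment) leaves a route to selection bias open. The size of any bias cannot be measured from the documents, and there is no evidence in them that steering would occur.

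The conclusion rests on the text alone. It would fall away if an operating procedure outside these documents already required numbered, opaque envelopes used in strict order, and kept the list holder out of recruitment. It should be settled before patients are entered, since bias at allocation cannot be corrected afterwards.

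**What to change.** Replace the Randomization and Type of randomization entries with one description:

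1. Delete "patients would be allocated to either of the groups by selecting names from sealed envelopes" and the pre-naming of envelopes.
2. Use one computer-generated block list, with block size not disclosed to those who recruit.
3. Load the list into sequentially numbered, opaque, sealed envelopes.
4. After consent and confirmed eligibility, each patient takes the next number in strict order. Identifier, date and time are written on the envelope before it is opened.
5. Add recruitment, eligibility decisions and order of entry to the activities from which the list holder is barred.

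Reconcile the stated time of randomisation with the stated time of dosing in the same edit.

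The cost is a few replacement sentences and slightly more envelope handling. The envelopes and the separate unblinded member already exist in the plan. Sample size and analysis are unchanged.
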